4.2 Trial Endpoints

Primary Endpoints

HPA axis

Subjects with serum cortisol level of less than 18 µg/dL at 30 minutes after ACTH challenge test at Week 4 and Week 8.

Calcium metabolism

Changes from Baseline to Week 4 and Week 8 in:

- Albumin-corrected serum calcium;
- Ratio of urinary calcium to creatinine*.

*Spot analysis, second morning urine sample

Secondary Endpoints

Plasma PK parameters (AUC_{0-t}, AUC₀₋₅, C_{max} and T_{max}) will be calculated at Week 4. The PK parameters AUC₀₋₅ and C_{max} will be calculated using standard formulas inserting the lower limit of quantification (LLOQ) for non-quantifiable levels of the analyte; therefore, AUC₀₋₅ will be an upper limit in case at least one time-point shows a non-quantifiable level of the analyte, and C_{max} will be an upper limit in case all time points show non-quantifiable levels of the analyte. For a given analyte, the PK parameters AUC_{0-t} and T_{max} will be calculated if at least one time-point shows a quantifiable level of the analyte. The PK parameters will be summarised using appropriate descriptive statistics including median, lower and upper quartiles, minimum and maximum.

Blood samples for PK assessments will be collected at

- SV2 (baseline sample)
- Week 2 (single time point before application of IP)
- Week 4; before application of IP and then at 1, 3, and 5 hours after the application.
- Week 8; (single time point. Subject should not apply IP on the day of the Week 8 visit)

The samples will be assayed for concentrations of the active ingredients (BDP and CAL) and for their main metabolites; MC1080 and betamethasone 17-propionate, respectively.

Safety Endpoints

Safety endpoints include the following:

- Adverse events (AEs) and serious adverse events (SAEs);
- Local skin reaction;

- Changes in safety laboratory test results;
- Changes in ECGs;
- Changes in vital signs and physical examinations

Other Endpoints

- The proportion of subjects with treatment success, defined as a minimum 2-point decrease from baseline in the PGA on the body (trunk and/or limbs), and with or without scalp at Week 4 and Week 8.
- Subject assessment of treatment convenience at Week 8 using a Psoriasis Treatment Convenience Scale.

5.0 SELECTION OF TRIAL POPULATION

5.1 Subject Population

It is planned to enroll approximately 30 subjects. The choice of sample size in this trial is based on regulatory considerations with respect to common practice in maximum use studies. For the PK population, the aim is to have at least 20 subjects included that have at least completed Week 4 (Visit 3).

An individual subject will be allowed to participate in the trial one time only. A rationale for the choice of sample size is provided in [Section 8.2](#) of this protocol.

A written informed assent will be signed and dated by the subject and an informed consent document (ICF) will be signed and dated by the parent(s) or legal guardian(s) before any trial-specified procedures are performed. Subjects will provide authorisation for use of their personal data in accordance with the applicable regulations regarding privacy and data protection.

5.2 Inclusion Criteria

Subjects must meet all the following criteria to be eligible for participation in the trial:

1. The parent(s), or legal guardian(s) (according to national law) have provided written informed consent following their receipt of verbal and written information about the trial;
2. The subject (according to national law) has provided written assent to the trial following their receipt of verbal and written information about the trial;
3. Generally healthy males or non-pregnant females, of any race or ethnicity, who are between 12 to 16 years, 11-month-old at SV1;
4. At Visit 1/Day 0, have a clinical diagnosis of plaque psoriasis (psoriasis vulgaris) of at least 6 months duration involving body (trunk and/or limbs), with or without scalp;

5. Have a treatment area between 10% and 30% of the BSA on the body (trunk and/or limbs) and scalp, excluding psoriatic lesions on the face, genitals, and intertrigenous areas, at Visit 1/Day 0;
6. Have a PGA of at least moderate severity on the treatment area;
7. A normal HPA axis function including a serum cortisol concentration above 4.5mcg/dl (160nmol/l) before ACTH-challenge and equal or above 18 mcg/dl (500 nmol/l) 30 minutes after ACTH challenge, at SV2;
8. A serum albumin-corrected calcium below the upper reference limit at SV2;
9. Female subjects must have a negative urine pregnancy test result at SV1, and if sexually active they must agree to use a highly effective method of contraception (i.e. a method with a failure rate of less than 1% per year when used consistently and correctly) for two months prior to Visit 1 and until the follow-up visit has been performed. Highly effective contraception allowed in this trial is defined as follows:
 - intrauterine device (IUD)
 - bilateral tubal occlusion
 - vasectomised partner (provided that is the sole sexual partner of the subject and that the vasectomised partner has received medical assessment of the surgical success.)
 - sexual abstinence (if in line with the preferred and usual lifestyle of the subject and defined as refraining from heterosexual intercourse during the entire period of the trial. Periodic methods of abstinence (e.g. calendar, ovulation, sympto-thermal, post-ovulation methods) are not accepted methods of contraception.)

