7.6 Laboratory Assessments

All clinical laboratory specimens will be analysed by a central licensed and accredited laboratory facility according to the laboratory's standard operating procedures (SOPs).

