6.2. Analysis Populations

The main subject samples of interest are defined as follows.

The 'All enrolled subjects': all subjects for whom Informed Consent/Assent were obtained:

The 'Allocated to treatment': all subjects for whom Informed Consent/Assent were obtained and who had successfully completed Screening procedures and to whom any amount of trial medication was dispensed.

The 'Safety population': all subjects who are enrolled in the trial and dispensed the trial medication at Visit 1/Day 0, excluding subjects who return all of the trial medication unused. The Safety population will be used for all safety analyses other than evaluation of the HPA-axis.

The 'PK population': all subjects in the Safety population who have received the planned application of treatment at the Week 4 visit and have had at least one blood draw for PK assessment at Week 4.

The 'HPA population': all subjects in the Safety population that show normal HPA function at SV2:

- Serum cortisol concentration above 4.5mcg/dl (160nmol/l) before ACTH-challenge and equal or above 18 mcg/dl (500 nmol/l) 30 minutes after ACTH challenge, at SV2.

The HPA population will be used for the HPA axis suppression analysis.

³ This section is based on the section 5.1 "Subject Population" and 8.2 "Sample Size and Power Considerations" of clinical study Protocol.

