7.2. Protocol Deviations

Number and percentage of subjects with at least one protocol deviation and at least one major protocol deviation will be tabulated by category and subcategory and overall (Allocated to treatment set). All protocol deviations will be listed (All Enrolled subjects).

Major protocol violations include but are not limited to:

- Informed consent not received or provided after the first study visit;
- Inclusion/exclusion criteria violations in subjects allocated to treatment;
- Use of prohibited concomitant medication or non-drug therapy that may affect study results or their interpretation;
- Week 4 assessments performed more than 14 days after the scheduled date;
- Week 8 assessments performed more than 14 days after the scheduled date;

Major protocol violations will be finalized and approved by MC2 at the data review meeting.

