APPENDIX 1 TFLs Shells

BMI=Body Mass Index; BSA=Body Surface Area; PGA= Physician Global Assessment.

N: the number of subjects in the Safety population.

n: the number of subjects within a specific category or the number of valid observations. Percentages are based on the corresponding number of valid observations.

[1] Baseline is the last non-missing assessment prior to the first dose of the study drug.

Path to the program code, date and time of output/ Datasets used/ Referenced Data Listings

Programming note:

Report the following visits: Screening V1, Screening V2, Visit 1 (Day 0), Baseline (where applicable).

Continue table for the following parameters:

- Physician global assessment of psoriasis severity (continuous);
- Height (cm);
- Weight (kg);
- Body mass index (BMI, kg/m²);
- Systolic blood pressure (mm Hg);
- Diastolic blood pressure (mm Hg);
- Pulse (beats/min);
- Oral temperature (C);
- Tympanic temperature (C);
- 25-Hydroxyvitamin D3 (ug/L);
- Serum Calcium Corrected for Albumin (mmol/L);
- Scalp BSA psoriatic involvement (%);
- Neck, Trunk and/or Limbs BSA psoriatic involvement (%);
- Total psoriatic involvement (%);
- Serum cortisol pre-stimulation (nmol/L);
- Serum cortisol post-stimulation (nmol/L);
- Investigator assessment of Erosion/ulceration in lesional area (0 (Absent), 1 (Mild), 2 (Moderate), 3 (Severe));
- Investigator assessment of Vesicles in lesional area (0 (Absent), 1 (Mild), 2 (Moderate), 3 (Severe));
- Investigator assessment of Erythema in perilesional area (0 (Absent), 1 (Mild), 2 (Moderate), 3 (Severe));

MC2-01-C6_STATISTICAL ANALYSIS PLAN_Final 3.0_07 September 2020

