APPENDIX 1 TFLs Shells

HPA Axis Suppression

MC2 Therapeutics
MC2-01-C6Table 14.3.4.1.1 Summary of ACTH Challenge Test
HPA population
Page X of X

| Serum Cortisol (nmol/L) | Total (N=XX) | |
|-------------------------|-----------------------|-----------------------|
| | Pre-stimulation | Post-stimulation |
| Baseline | | |
| n | XX | XX |
| Mean [95% CI] | XX.XX [XX.XX - XX.XX] | XX.XX [XX.XX - XX.XX] |
| SD | XX.XX | XX.XX |
| Median | XX.XX | XX.XX |
| Q1, Q3 | XX.XX, XX.XX | XX.XX, XX.XX |
| Min, Max | XX.X, XX.X | XX.X, XX.X |
| Visit 3 / Week 4 | | |
| n | XX | XX |
| Mean [95% CI] | XX.XX [XX.XX - XX.XX] | XX.XX [XX.XX - XX.XX] |
| SD | XX.XX | XX.XX |
| Median | XX.XX | XX.XX |
| Q1, Q3 | XX.XX, XX.XX | XX.XX, XX.XX |
| Min, Max | XX.X, XX.X | XX.X, XX.X |
| Visit 5 / Week 8 | | |
| n | XX | XX |
| Mean [95% CI] | XX.XX [XX.XX - XX.XX] | XX.XX [XX.XX - XX.XX] |
| SD | XX.XX | XX.XX |
| Median | XX.XX | XX.XX |
| Q1, Q3 | XX.XX, XX.XX | XX.XX, XX.XX |
| Min, Max | XX.X, XX.X | XX.X, XX.X |
| Follow-up | | |
| n | XX | XX |
| Mean [95% CI] | XX.XX [XX.XX - XX.XX] | XX.XX [XX.XX - XX.XX] |
| SD | XX.XX | XX.XX |
| Median | XX.XX | XX.XX |
| Q1, Q3 | XX.XX, XX.XX | XX.XX, XX.XX |
| Min, Max | XX.X, XX.X | XX.X, XX.X |

MC2-01-C6_STATISTICAL ANALYSIS PLAN_Final 3.0_07 September 2020

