**MC2-01-C6_STATISTICAL ANALYSIS PLAN_Final 3.0_07 September 2020**
APPENDIX 1 TFLs ShellsMC2 Therapeutics
MC2-01-C6**Table 14.3.4.1.2 Incidence of HPA Axis Suppression**
HPA population
Page X of X

| | | Total (N = XX) |
|-----------------------------------|-----------------------------------|--------------------------------------|
| HPA axis suppression | | |
| Overall | n' (%) [1] n (%) [2] 95% CI | XX (XX.X) XX (XX.X) XX.X, XX.X |
| Visit 3 / Week 4 | n' (%) [1] n (%) [2] 95% CI | XX (XX.X) XX (XX.X) XX.X, XX.X |
| Visit 5 / Week 8 | n' (%) [1] n (%) [2] 95% CI | XX (XX.X) XX (XX.X) XX.X, XX.X |
| HPA axis suppressed at Week 4 | n' (%) [3] n (%) [2] 95% CI | XX (XX.X) XX (XX.X) XX.X, XX.X |
| HPA axis not suppressed at Week 4 | n' (%) [3] n (%) [2] 95% CI | XX (XX.X) XX (XX.X) XX.X, XX.X |

CI=Confidence Interval; HPA=Hypothalamic-pituitary-adrenal.

N: the number of subjects in the HPA population. n: the number of subjects within a specific category. n': the number of valid observations.

[1] Subjects having any post-baseline values (for 'Overall' category) or values at the corresponding visit. Percentage is calculated as $(100 \times n/N)$.

[2] Percentages are based on the corresponding number of valid observations.

[3] Subjects with corresponding HPA suppression status at Week 4 having values at Visit 5 / Week 8. Percentage is calculated based on number of subjects with corresponding HPA suppression status at Week 4.

Confidence interval is calculated using Clopper-Pearson method.

Adrenal suppression is defined as the 30-minute post-stimulation serum cortisol level below 18 ug/dL (500 nmol/L).

Data MATRIX

SF_STAT001_ver 2_Eng
Approval Date 19 July 2017

MC2-01-C6_STATISTICAL ANALYSIS PLAN_Final 3.0_07 September 2020

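### The pre-ACTH cortisol cut-off of 4.5 mcg/dl (160 nmol/l) contradicts the documents' own 18 mcg/dl = 500 nmol/l, and nothing says which unit governs eligibility and the HPA population

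*Protocol*

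**What the plan says.** Criterion 7 in Protocol 5.2 defines normal HPA function at SV2 as "a serum cortisol concentration above 4.5mcg/dl (160nmol/l) before ACTH-challenge and equal or above 18 mcg/dl (500 nmol/l) 30 minutes after ACTH challenge". Protocol 8.3 defines the HPA population only as Safety-population subjects with normal HPA function at SV2 and gives no number. SAP 6.2 supplies the numbers: "Serum cortisol concentration above 4.5mcg/dl (160nmol/l) before ACTH-challenge and equal or above 18 mcg/dl (500 nmol/l) 30 minutes after ACTH challenge".

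The 18/500 pair also appears in Protocol 7.6.2, in SAP 9.5 and in the footnote to SAP Table 14.3.4.1.2. The 4.5/160 pair appears only in Protocol 5.2 and SAP 6.2.

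SAP 7.2 counts as major violations "Inclusion/exclusion criteria violations in subjects allocated to treatment".

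The SAP shells for Tables 14.1.8 and 14.3.4.1.1 and Listing 16.2.8.7 show cortisol in nmol/L.

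**The concern.** A conversion between mass and molar units for a single hormone is one constant. Criterion 7 uses two different constants in the same sentence, so the pre-ACTH limit has two values. Neither document says which applies when they disagree. The nmol/L labels in the shells set a display unit. A programmer working with nmol/L data could apply 160 as printed or convert 4.5 mcg/dl to 125, and the text supports either reading.

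For a subject between the two values, the choice decides:

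- whether the subject was eligible;
- whether a treated subject is a major inclusion violation;
- whether the subject belongs to the HPA population, which is the analysis set for a primary endpoint and for the baseline cortisol summary in Table 14.3.4.1.1.

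SAP 6.1 plans the interim analysis after 7 treated subjects complete the study, and SAP 6.4 says the interim report informs whether the trial is closed or re-activated. One reclassified subject would be 1/7, about 14% of them.

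**Working it through.** **Inputs**, all from Protocol 5.2 criterion 7 and SAP 6.2: pre-ACTH limit 4.5 mcg/dl, also printed as 160 nmol/l; post-ACTH limit 18 mcg/dl, also printed as 500 nmol/l.

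**Implied conversion factors**

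- Post-ACTH pair: 500 / 18 = 27.78 nmol/l per mcg/dl.
- Pre-ACTH pair: 160 / 4.5 = 35.56 nmol/l per mcg/dl.

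**The stated equivalence of 4.5 and 160 is not reproduced**

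- 4.5 × 27.78 = 125.0 nmol/l, not 160.
- 160 / 27.78 = 5.76 mcg/dl, not 4.5.
- Ratio: 160 / 125 = 1.28. Band: 160 − 125 = 35 nmol/l.
- In the other direction, 18 × 35.56 = 640 nmol/l, not 500.

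**Could rounding explain it?** Take 18 as low as 17.5 and 4.5 as high as 4.55, the directions that most favour agreement. The lowest value that rounds to 160 at the nearest 10 is 155.

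| 500 rounded to the nearest | Largest nmol/l value for 4.5 mcg/dl | Range of the ratio, all four numbers at their rounding limits |
|---|---|---|
| 10 | 505 / 17.5 × 4.55 = 131.3 | 1.18 to 1.39 |
| 100 | 550 / 17.5 × 4.55 = 143.0 | 1.08 to 1.52 |

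Both largest values are below 155, and the ratio stays above 1 throughout.

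**Who is affected.** By the 18/500 pair, a pre-ACTH value above 125 and up to 160 nmol/l (above 4.5 and up to 5.76 mcg/dl) passes in mcg/dl and fails in nmol/l.

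**Illustration only.** Assume that all 7 treated interim subjects are otherwise in the HPA population with a valid ACTH test, exactly one is in the band, and nobody is suppressed. The estimate is 0% either way. With zero events the exact (Clopper-Pearson) 95% upper limit is 1 − 0.025^(1/n):

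- n = 7: 41.0%
- n = 6: 45.9%

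**The case against.** The arithmetic is not in dispute. The case against giving it weight is about consequence:

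- Suppression after baseline depends only on the 30-minute value. No test, success criterion or sample size uses the pre-ACTH limit.
- An affected subject must fall in a narrow band and still reach 500 nmol/l, a rise of at least 500 − 160 = 340 nmol/l. Nothing shows that such a subject exists.
- Controls are in place. Protocol 7.6 states that "All clinical laboratory specimens will be analysed by a central licensed and accredited laboratory facility", Listing 16.2.1.1 gives a reason for each exclusion from the HPA population, and SAP 7.2 says "Major protocol violations will be finalized and approved by MC2 at the data review meeting". The SAP revision history shows that version 3.0 followed a data review meeting, so eligibility conflicts may already have been examined.
- The laboratory manual or the eCRF, neither supplied, may hold the limit that was actually applied.
- The 0/7 versus 0/6 comparison needs several conditions together, and no documented decision threshold lies between the two limits.

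Much of this stands as a limit on size. The suppression threshold is untouched, the number affected may be zero, and the comparison is only an illustration. It does not remove the problem. The controls can make a borderline subject visible, but none supplies the threshold, and version 3.0 still carries both values. An unseen operating rule would help the sponsor reconcile the values, but it does not correct the text. The question of which cut-off was used at screening is a good one and belongs in the fix.

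**Conclusion.** The concern holds. On the documents' own 18/500 pair, the two printed pre-ACTH cut-offs are 125 and 160 nmol/l, a factor of 1.28. Allowing for rounding, the factor is 1.18 to 1.39, or 1.08 to 1.52 if 500 is good only to the nearest hundred. The effect is confined to eligibility, major-deviation status, membership of the HPA population and the summaries built on that set. The documents give no cortisol distribution, so the number of subjects involved cannot be estimated. They also do not show which value was intended, and this review does not choose between them. It should be fixed because the threshold defines the analysis set of a primary endpoint and, if recruitment resumes, would be used to screen new subjects.

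**What to change.** 1. Ask the sites and the central laboratory which pre-ACTH limit was applied at SV2, so that the analysis rule does not differ unknowingly from the eligibility rule used.
2. Have the sponsor reconcile the two values and state one governing value in one unit in SAP 6.2, with a correct conversion. The trial is open-label and a data review meeting has apparently been held, so settle this without reference to individual SV2 results. Derive the HPA-population flag from that value.
3. Then use planned Listing 16.2.8.7 to check every SV2 pre-stimulation value from 124 to 160 nmol/l for consistent eligibility, deviation and HPA-population status. The lower end is 495 / 18 × 4.5 = 123.75, which is 125 with a margin for rounding 500 to the nearest 10. Starting at 450 / 18 × 4.5 = 112.5 would also cover rounding to the nearest 100. Report the number found, including zero.
4. If the trial is re-activated, correct criterion 7 in Protocol 5.2 as well.

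The cost is one SAP line and a check of a listing already planned. The SAP Introduction allows revision before the interim database lock. If the lock has passed, it requires deviations from the SAP to be explained in the study report, and it provides for a separate SAP for any final analysis. The protocol change is one line, but it needs an approved amendment under Protocol 9.1.

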5.3 Exclusion Criteria

Subjects who fulfil any of the following criteria will be ineligible to participate in the trial:

1. Have a current diagnosis of unstable forms of psoriasis, including erythrodermic or pustular psoriasis;
2. Other inflammatory skin disease in the treatment area that may confound the evaluation of the psoriasis vulgaris (e.g., atopic dermatitis, contact dermatitis, tinea corporis);
3. Presence of infections in the treatment area (e.g. skin infection with bacteria (including tuberculosis), viruses, parasites or fungi) or skin manifestations of atrophic skin, atrophic striae, skin vein fragility, ichthyosis, acne vulgaris, acne rosacea, rosacea, ulcers and wounds in the treatment area.
4. Presence of pigmentation, extensive scarring, pigmented lesions or sunburn in the treatment areas, which could interfere with the rating of efficacy parameters;
5. Planned excessive or prolonged exposure to either natural or artificial sunlight, including tanning booths, sun lamps, etc;

6. Use of phototherapy (psoralen + ultraviolet A radiation [PUVA] and ultraviolet B radiation [UVB]) within 4 weeks prior to SV2 and during the trial;
7. Current or past history of disorders of calcium metabolism associated with hypercalcemia, vitamin D toxicity, severe renal insufficiency, or severe hepatic disorders;
8. Oral calcium supplements, vitamin D supplements, bisphosphonates or calcitonin within 4 weeks prior to SV2.
Note: Stable doses of oral vitamin D supplementation ≤ 400 IU/day is permitted provided there are no dose adjustments during the trial period;
9. Planned initiation of, or changes to concomitant medication that could affect calcium metabolism (e.g., antacids, thiazide and/or loop diuretics, antiepileptics) during the trial;
10. Use or planned initiation of estrogen and/or progestogen therapy (e.g. hormonal contraception) during the trial;
11. Strong systemic cytochrome P450 3A4 (CYP 3A4) inhibitors or inducers (e.g., clarithromycin, telithromycin, nefazodone, itraconazole, ketoconazole, atazanavir, darunavir, indinavir, lopinavir, nelfinavir, ritonavir, saquinavir, tipranavir, rifampicin, phenobarbital, phenytoin) within 4 weeks prior to SV2 and during the trial period;
12. Use of topical treatments (eg, corticosteroids, vitamin D analogs, retinoids, PDE4 inhibitors, salicylic acid, pimecrolimus, tacrolimus, anthralin, tar), except for emollients and non-medicated shampoos, with a possible effect on psoriasis within 2 weeks prior to SV2 and during the trial period;
13. Systemic treatment with biological therapies, whether marketed or not, with a possible effect on psoriasis vulgaris within the following time period prior to SV2 and during the trial period;
 - etanercept – within 4 weeks
 - adalimumab, alefacept, infliximab – within 8 weeks
 - ustekinumab – within 16 weeks
 - other products – within 4 weeks/5 half-lives (whichever is longer)In general, subjects who are candidates for biological or other systemic therapy are excluded from the trial.
14. Initiation of, or expected changes to, concomitant medication that may affect psoriasis (e.g., beta-blockers, chloroquines, lithium, and angiotensin converting enzyme [ACE] inhibitors) and during the trial period;
15. Any of the following conditions, whether known or suspected:

- Clinically diagnosed depression where the subject is in current treatment with medication approved for treatment of depression
- Endocrine disorders (e.g. Cushing's disease or Addison's disease) known to affect cortisol levels or HPA axis integrity.
- Non-nocturnal sleep patterns (e.g. irregular sleep patterns)

16. Use of systemic medication that suppresses the immune system (e.g., methotrexate, retinoids, PDE4 inhibitors, corticosteroids (excluding inhaled, nasal, auricular or ocular corticosteroids), ciclosporin (cyclosporine), and other systemic chemotherapeutic antineoplastic therapy) within 4 weeks prior to the SV2 and during the trial period;

17. Use of live vaccines 4 weeks before SV2 and during the trial period;

18. Known human immunodeficiency virus (HIV) infection, active hepatitis B or hepatitis C;

19. Known or suspected of hypersensitivity to any component of the test product;

20. Known allergic asthma, serious allergies or allergies where recurrent acute or chronic treatment is necessary (excluding hay fever);

21. Have any chronic or acute medical condition that, in the opinion of the investigator, may pose a risk to the safety of the subject, or may interfere with the assessment of safety or efficacy in this trial;

22. Require the use of any concomitant medication that, in the investigator's opinion, has the potential to cause an adverse effect when given with the IP or will interfere with the interpretation of the trial results;

23. Females who are pregnant, breast feeding, or planning a pregnancy;

24. Subject with known abnormal reduction in muscle mass, as judged by the investigator;

25. Participation in another clinical trial or received an IP or non-marketed drug substance within 30 days prior to SV2;

26. Previously enrolled in this trial;

27. In the opinion of the (sub)investigator, the subject is unlikely to comply with the clinical trial protocol;

